1.4 BENEFIT - RISK ASSESSMENT

The overall benefits and safety profile of BI 456906 have been outlined in previous sections. More information on the benefits, risks, and known AEs will be presented in the Investigator's Brochure.

1.4.1 Benefits

Based on the currently available data, in otherwise healthy volunteers with obesity or overweight, dual agonism at the GLP1R and GCGR is expected to result in superior body weight loss and maintenance compared to GLP1R agonism alone, [REDACTED]

[REDACTED] Thus, subjects to be treated with BI 456906 are expected to achieve improved weight management results compared to prior to their trial participation.

1.4.2 Risks

There is no identified risk for BI 456906, based on the toxicology programme or any clinical trials conducted for this product to date. There are three important potential risks based on other GLP-1 receptor agonists currently approved, providing information on identified and potential risks in molecules of this class. The three important potential risks include medullary thyroid cancer (c-cell carcinogenicity), pancreatic cancer, and acute pancreatitis.

The risk for patients caused by participation in the trial, including the study procedures and exposure to the study drug, are reasonably low and do not outweigh the potential benefits. The expected side effects are known to be temporary, dose dependent, easy to monitor and manageable in clinical trials.

Table 1.4.2:1 Overview over trial related risks

| Possible or known risks of clinical relevance for this trial | Summary of data, rationale for the risk | Mitigation strategy |
|--|--|---|
| Investigational Medicinal Product | | |
| Gastrointestinal disorders, or Metabolism and nutrition disorders | Well-known side effects for GLP1-R agonist-based therapies | Slow and careful dose escalation. Instructions to be given |
| Cardiac disorders | Well-known side effects for GLP1-R agonist-based therapies | Centralised Electrocardiogram (ECG) monitoring will be performed at screening, randomization and within predefined intervals during the trial, and criteria for heart rate, QT prolongation and cardiac conduction disorders are defined. |
| Acute pancreatitis | To date there is no evidence that BI456906 causes such adverse events. | An extensive safety laboratory will be performed. |
| Medullary thyroid carcinoma (MTC), or Multiple endocrine neoplasm (MEN) Type 2 | Well-known side effects for GLP1-R agonist-based therapies * Well-known side effects for GLP1-R agonist-based therapies, and well-known adverse event of rapid significant weight loss | Timely detection, evaluation, and follow-up of laboratory alterations in selected liver laboratory parameters to ensure patients' safety. |
| Acute biliary disease* | | |
| Systemic hypersensitivity reaction | After administration of any biologic agent or protein, there is a possibility of occurrence of adverse immune reactions which can be local (e.g redness, pruritus, and or swelling at the injection site) or systemic (e.g. anaphylactic reactions). | Patients with a history of allergy/hypersensitivity to the systemically administered trial medication agent or its excipients are excluded from the trial. In case of systemic hypersensitivity reactions including anaphylactic reaction emerging during or after administration of trial medication, the investigator should consider in accordance with severity of the reaction and local standard of care to interrupt and treat the condition. |

Table 1.4.2:1 Overview over trial related risks (cont.)

| | | |
|--|--|--|
| Trial procedures | | |
| Insufficient weight loss | Patients who will receive placebo may not achieve sufficient weight loss during the trial. | Patients in placebo group will remain on standard of care that includes diet and exercise counselling. |
| Administration site conditions | Well-known side effects for injectables | Instructions to be given Injection site will be monitored during the physical exam in every visit |
| Other risks | | |
| Drug-induced liver injury (DILI) | Rare but severe event, thus under constant surveillance by sponsors and regulators | Timely detection, evaluation, and follow-up of laboratory alterations in selected liver laboratory parameters to ensure patients' safety |
| Acute kidney injury (pre-renal) | Related to severe GI AEs of GLP-1RA class (severe vomiting may cause dehydration) | -In case of vomiting, nausea and diarrhea, increase fluid intake - Monitor decreased renal function |
| Suicide risk, depression and mood disorder | Not observed in clinical trials so far. BI456906 could potentially act on central GLP-1 receptor. | Columbia Suicide Severity Rating Scale (C-SSRS) will be applied at every visits; |

These side effects can be reduced by careful dose escalation, are known to be dose dependent, are easy to monitor, and manageable in clinical trials.

In this trial the following safety measures will be applied in order to minimize the risk for trial patients:

An extensive safety laboratory will be performed.

- Patients in all groups, including placebo group will receive standard of care that includes diet and exercise counselling.
- There are no risks expected by stopping the trial medication during the trial.
- Centralised Electrocardiogram (ECG) monitoring will be performed at screening, randomization and within predefined intervals during the trial, and criteria for heart rate, QT prolongation and cardiac conduction disorders are defined.
- Instructions are to be given to the patients to help improve tolerability especially during escalation phase. In addition, patients who do not tolerate the assigned escalation schedule, can modify dose escalation schedule. Details are described in [section 4.1.4](#).
- During the trial, patients will be under medical observation and thoroughly monitored for both expected and unexpected AEs including administration and evaluation of the Columbia-Suicide Severity Rating Scale (C-SSRS).
- Paediatric patients (less than 18 years old) are excluded from the trial.
- Females of childbearing potential who are pregnant, breast-feeding or intend to become pregnant or are not using an adequate contraceptive method throughout the

trial including the 4-week follow-up period are excluded from the trial ([Section 4.2.2.2](#))

- To continue the assessment of the safety of BI 456906, adjudication of some events will be performed in that trial. The progress of the trial will also be assessed at regular intervals by an independent Data Monitoring Committee (DMC). Further details are described in [Section 8.7](#), the adjudication charter and the DMC charter.

Although rare, a potential for drug-induced liver injury (DILI) is under constant surveillance by sponsors and regulators. Therefore, this trial requires timely detection, evaluation, and follow-up of laboratory alterations in selected liver laboratory parameters to ensure patients' safety. [Section 5.2.6.1.4](#) provides guidance for the investigators on how to evaluate and treat patients with suspected DILI.

Based on the pharmacological mechanism of BI 456906, the review of the non-clinical and clinical data available so far for this compound and considering the clinical and post-marketing data derived from the GLP-1 receptor agonists available on the market, there is no indication that BI 456906 could increase the risk of severe viral infections such as SARS-CoV-2.

2. TRIAL OBJECTIVES AND ENDPOINTS

The overall purpose of this trial is to assess the efficacy on weight loss and maintenance, and tolerability of four different doses of BI 456906 compared to placebo in patients with obesity or overweight (BMI ≥ 27 kg/m²), without type 1 or type 2 diabetes, in order to characterize the dose-response relationship within the therapeutic range, and to select the target dose(s) for phase III clinical development. The results of this dose-finding study will serve as Proof of Clinical Concept in patients with obesity or overweight.

2.1 MAIN OBJECTIVES, PRIMARY AND SECONDARY ENDPOINTS

2.1.1 Main objectives

This trial will characterize the dose response curve for BI 456906 in patients with BMI ≥ 27 kg/m² (without diabetes) by assessing 4 doses and placebo. The response is defined as the percentage change from baseline in body weight at Week 46.

The main trial objectives are to demonstrate a non-flat dose response curve, to evaluate the size of the treatment effect (using the difference in mean percentage change between BI 456906 and placebo at Week 46), and to characterise the dose-response relationship.

The primary treatment comparison will be randomised, without regard to whether patients discontinued treatment early (and whether they subsequently received any permitted anti-obesity treatments), or whether patients started the maintenance period with a lower dose than the dose that they were randomised to.

2.1.2 Primary endpoint(s)

The primary endpoint is:

- Percentage change in body weight (%) from baseline to week 46

2.1.3 Secondary endpoint(s)

Secondary endpoints are:

- Weight loss of $\geq 5\%$ of baseline weight at week 46
- Weight loss of $\geq 10\%$ of baseline weight at week 46
- Weight loss of $\geq 15\%$ of baseline weight at week 46
- Absolute change in body weight (kg) from baseline to week 46
- Absolute change in waist circumference (cm) from baseline to week 46
- Absolute change in systolic blood pressure (mmHg) from baseline to week 46
- Absolute change in diastolic blood pressure (mmHg) from baseline to week 46

3. DESCRIPTION OF DESIGN AND TRIAL POPULATION

3.1 OVERALL TRIAL DESIGN

This is a 46 week randomised, double-blind, parallel-design, placebo-controlled, multi-national and multi-centre study with 4 different maintenance doses (ranging from 0.6mg/week to 4.8mg/week) in patients with obesity or overweight ($BMI \geq 27\text{kg/m}^2$), and without diabetes. Patients in all treatment arms including placebo will receive counselling for a reduced-calorie diet with an energy deficit of approximately 500 kcal/day by a dietician, as well as increased physical activity counselling (recommended minimum 150 minutes/week) by a qualified person on a monthly basis.

Participants will be randomly assigned to one of the 4 active dose arms of BI 456906 or placebo at a 1:1:1:1 ratio.

The different treatment arms and the dose escalation scheme are presented in [Table 4.1.4:1](#).

There will be a screening period of minimum one week (time needed to obtain all examination results), that could be extended up to 12 weeks as needed to check eligibility criteria. The lab criteria “at screening” remain sufficient for checking lab eligibility criteria at randomisation.

The treatment duration is 46 weeks in total including a dose escalation phase of 20 weeks to minimize GI side effects of BI 456906. This is followed by a 26-week maintenance phase, and a 3-week (4 weeks after last dose) follow-up period.

[figure not shown]

Figure 3.1:1 Dose escalation scheme

Screening period: Minimum 1 week, and up to 12 weeks maximum

Randomisation period:

- Dose escalation phase: up to 20 weeks (see [section 4.1.4](#))
- Maintenance phase: 26 weeks

Follow up: 4 weeks after last drug injection

One interim analysis will be performed during the trial. Please refer to [section 7.2.7](#)

3.2 DISCUSSION OF TRIAL DESIGN, INCLUDING THE CHOICE OF CONTROL GROUP(S)

This trial is designed to evaluate safety, tolerability and efficacy on weight reduction and maintenance of BI 456906 in patients with obesity or overweight using multiple escalation schemes and doses, and will support dose selection for phase 3 clinical development of BI 456906 in the indications of chronic weight management in patients with obesity or overweight. The inclusion of the placebo comparator helps to better characterise the nature of any dose response.

A treatment duration of 46 weeks, including at least 26 weeks with stable dose, is considered to be sufficient to assess dose response on clinically meaningful weight reduction required by regulatory authorities. Furthermore, a 46-week trial period is considered to be sufficient to characterise the safety and tolerability profile of BI 456906.

Choice of endpoints:

In patients with overweight/obesity, weight loss can be directly associated with benefits in health outcomes. The primary endpoint is a direct measure of body weight change based on the regulatory guidance. Key secondary endpoints will also look at weight loss, absolute and two different categorical responder thresholds.

It is well documented that certain thresholds of categorical weight loss (>5%, >10% >15%) are associated with improved body weight related metabolic profiles and/or related co-morbidities.

In clinical practice, waist circumference is used as an indirect measure of visceral fat content, which when increased is associated with an elevated risk for metabolic abnormalities. Measuring waist circumference can be a means to confirm that reductions in waist circumference are associated with the expected improvements in metabolic parameters related to weight reduction.

Data Monitoring Committee

A Data Monitoring Committee (DMC), independent from the Sponsor, will be established to review the unblinded safety data at intervals, and to recommend to the Sponsor whether to continue, modify, or stop the trial. The tasks and responsibilities of the DMC members will be detailed in the DMC charter. See [section 8.7](#)

Clinical Event Committee

Prospective adjudication of some events will take place through an independent, blinded, external Clinical Event Committee (CEC) as described in [section 5.2.6.1.5](#). Details on the

composition of the committee, its procedures and interactions will be provided in a separate CEC charter.

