| Trial objective(s) | The primary objective is to demonstrate proof of clinical concept with respect to a non-flat dose response curve and to define a suitable dose escalation scheme and dose range for BI 456906 regarding safety, tolerability, and efficacy, for further pivotal testing in phase 3 studies. |
| Trial endpoints | Primary endpoint Percentage change in body weight (%) from baseline to week 46 Secondary endpoints 
• Weight loss of $\geq 5\%$ of baseline weight at week 46• Weight loss of $\geq 10\%$ of baseline weight at week 46• Weight loss of $\geq 15\%$ of baseline weight at week 46• Absolute change in body weight (kg) from baseline to week 46• Absolute change in waist circumference (cm) from baseline to week 46• Absolute change in systolic blood pressure (mmHg) from baseline to week 46• Absolute change in diastolic blood pressure (mmHg) from baseline to week 46 |
| Trial design | Randomized, double blind, parallel group, placebo-controlled trial |
| Total number of patients randomised | 350 |

| | |
|--------------------------------------|---|
| Number of patients on each treatment | 70 |
| Diagnosis | Obesity or Overweight defined as BMI \geq 27kg/m ² |

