4.1.4 Drug assignment and administration of doses for each patient

Table 4.1.4:1 Dose Escalation Scheme

| Dose group | Weekly dose in (mg) | | | | | | | | | | | | | | | | | | | |
|-------------------|---|---|-----|---|-----------------|---|-----------------|---|-----------------|----|--|----|-----------------|----|-----------------|----|-----------------|----|-----------------|----|
| | Fixed escalation (titration is not allowed) | | | | | | | | | | Flexible escalation (titration is allowed) | | | | | | | | | |
| Week of treatment | 1 | 2 | 3 | 4 | 5 | 6 | 7 | 8 | 9 | 10 | 11 | 12 | 13 | 14 | 15 | 16 | 17 | 18 | 19 | 20 |
| Escalation | | | 1st | | 2 nd | | 3 rd | | 4 th | | 5 th | | 6 th | | 7 th | | 8 th | | 9 th | |
| BI A | 0.3 | | 0.6 | | 0.6 | | 0.6 | | 0.6 | | 0.6 | | 0.6 | | 0.6 | | 0.6 | | 0.6 | |
| BI B | 0.3 | | 0.6 | | 0.9 | | 1.2 | | 1.2 | | 1.8 | | 1.8 | | 2.4 | | 2.4 | | 2.4 | |
| BI C | 0.3 | | 0.6 | | 0.9 | | 1.2 | | 1.2 | | 1.8 | | 2.4 | | 3.0 | | 3.6 | | 3.6 | |
| BI D | 0.3 | | 0.6 | | 0.9 | | 1.2 | | 1.8 | | 2.4 | | 3.3 | | 4.2 | | 4.8 | | 4.8 | |

Fixed dose escalation phase (week 1- week 10)

During this phase the patient will receive planned dose as described Table 4.1.4:1 and titration within the dose group will not be allowed. Patients who cannot tolerate study drug during this period despite of all the efforts taken, will be discontinued from treatment.

Tolerability assessment after 10 weeks

Tolerability will be assessed after 10 weeks of treatment prior to dosing (visit 7). Patients who cannot tolerate medication in the week after dosing of week 10, will not continue titration to the next step, but will be moved to the next lower dosing available at week 11 and continue with this new scheme for the remaining visits

- Patients of Group D will then follow scheme of group C
- Patients of Group C and B will then follow scheme of group A
- For patients of group A, there is no lower dose possible. They will be maintained with same scheme, and if they again cannot tolerate at next visit they will be discontinued

Flexible dose escalation phase (week 11- week 20)

During this time, the investigator should make every effort to follow every two weeks dose escalation however, adjusting dosing scheme based on the patient tolerability of GI AEs will be allowed, in a blinded manner, as per the below:

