AEs will be coded using the version of the MedDRA coding dictionary in force at final DBL. The frequency of patients with all AEs will be summarised by treatment, primary system organ class (SOC) and preferred term (PT). A patient with multiple on-treatment occurrences of the same preferred term meeting the criteria for inclusion in the table will be counted only once in these tabulations. SOC's will be sorted by descending overall frequency; PT's will be sorted by descending overall frequency (within SOC). The summary of all AEs will be presented:

- Using actual maintenance treatment, with the treatment period pooled across, and split into, dose escalation and maintenance periods, respectively.

- Using planned maintenance treatment, with the treatment period pooled across dose escalation and maintenance periods only.

The AE summary by primary SOC and PT will also be repeated for each of the following, using actual maintenance treatment with the treatment period pooled across dose escalation and maintenance periods, only:

- AEs leading to treatment discontinuation
- Serious AEs
- Investigator-defined drug-related AEs
- Drug-related serious AEs.

An additional table will present the frequency of patients with AEs by worst intensity (mild, moderate, severe) and by primary SOC and PT. Where no events meet the criteria for inclusion in one of these tables, the table will be shown as indicating no events of that intensity have occurred.

The following tables will be produced by baseline body weight subgroup (< 100 / ≥ 100 kg):

- Overall AE summary
- Summary of all AEs by primary SOC and PT
- Summary of AEs leading to treatment discontinuation by primary SOC and PT.

For disclosure of AE data on ClinicalTrials.gov, the frequency of patients with non-serious AEs occurring with an incidence of greater than 5% (PT occurring in more than 5% of treated patients in one or more treatment groups) will be summarised by treatment, primary SOC and PT. The frequency of patients with serious AEs and drug related serious AEs will also be summarised respectively.

For disclosure of AE data in the EudraCT register, the frequency of patients with AEs, the frequency of patients with non-serious AEs with an incidence of greater than 5% (as above) and the frequency of patients with serious AEs will be summarised. Furthermore, the total number of treated patients by country and by age group will be summarised.

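### No AE table in the visible SAP compares the randomised escalation schemes over the weeks in which their doses differ, although defining a suitable scheme is part of the primary objective

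*Protocol*

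**What the plan says.** The synopsis states the primary objective partly as "to define a suitable dose escalation scheme and dose range for BI 456906 regarding safety, tolerability, and efficacy". Protocol section 3.2 describes the evaluation as "using multiple escalation schemes and doses, and will support dose selection for phase 3 clinical development". Section 3.1 fixes the time frame: "The treatment duration is 46 weeks in total including a dose escalation phase of 20 weeks".

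Table 4.1.4:1 sets out the schemes in two-week steps. The rows begin "BI B | 0.3 | | 0.6 | | 0.9 | | 1.2 | | 1.2 | | 1.8 | | 1.8", "BI C | 0.3 | | 0.6 | | 0.9 | | 1.2 | | 1.2 | | 1.8 | | 2.4" and "BI D | 0.3 | | 0.6 | | 0.9 | | 1.2 | | 1.8". Doses follow the table without adjustment to week 10. From week 11 patients may be moved to a lower scheme or held on a dose for a third week.

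SAP 7.8.1 counts patients, not events. For the tables by system organ class and preferred term, "A patient with multiple on-treatment occurrences of the same preferred term meeting the criteria for inclusion in the table will be counted only once". The overall summary and the table of all AEs are split into escalation and maintenance by actual maintenance treatment. By planned treatment, both are given only with the two periods pooled. The exposure-adjusted summary ends a patient's time at risk at the first on-treatment event.

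**The concern.** If a scheme is to be chosen on tolerability, the informative weeks are those in which the schemes give different doses. A table that covers all 20 weeks and counts each patient once per term mixes those weeks with a long stretch of identical dosing. A patient who had nausea on the shared doses is already in the count and adds nothing when it returns at a step specific to scheme C or D. The table also cannot show at which step events began.

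The grouping adds to this. Someone randomised to D who stops or steps down is tabulated under a lower dose, so AEs on the steepest scheme can appear in the column of a gentler one. At stake is how clearly the final report can say which scheme to take forward. The primary efficacy analysis is not affected.

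**Working it through.** **1. Where the schemes differ (Protocol Table 4.1.4:1, weekly dose in mg).**

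| Weeks | 1-2 | 3-4 | 5-6 | 7-8 | 9-10 | 11-12 | 13-14 | 15-16 | 17-18 | 19-20 |
|---|---|---|---|---|---|---|---|---|---|---|
| B | 0.3 | 0.6 | 0.9 | 1.2 | 1.2 | 1.8 | 1.8 | 2.4 | 2.4 | 2.4 |
| C | 0.3 | 0.6 | 0.9 | 1.2 | 1.2 | 1.8 | 2.4 | 3.0 | 3.6 | 3.6 |
| D | 0.3 | 0.6 | 0.9 | 1.2 | 1.8 | 2.4 | 3.3 | 4.2 | 4.8 | 4.8 |

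D matches B and C for 8 of 20 weeks (40%). B matches C for 12 of 20 weeks (60%). Divergence starts at week 9 for D and at week 13 for B versus C. Scheme A shares only weeks 1-4 with the others.

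**2. What each planned display can show about the weeks after divergence.**

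- Overall AE summary, and all AEs by preferred term: whole escalation period as one block, a patient counted once (per term in the second table). A late event under a new term is still counted in the second table; a recurrence of the same term is not.
- Worst intensity: a later, more severe event would register, but with no date and no stated period split.
- Exposure-adjusted summary: stops at the first event and has no time bands.
- Kaplan-Meier plot of time to treatment discontinuation, and disposition by period (SAP section 7): these carry timing, but only for events that end treatment.

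**3. Which group a patient is counted in (SAP 6.1.3).** The doses 3.3 mg and 4.2 mg occur only in scheme D. Under Table 6.1.3:1, a patient who stops at either is assigned to 3.6 mg. A scheme D patient who stops at 1.8 mg, the first step at which D differs, is assigned to 2.4 mg. A patient moved from D to C at week 11 who starts maintenance on 3.6 mg is also assigned to 3.6 mg, so AEs from weeks 9-10 on scheme D are tabulated there. The planned-treatment tables avoid this reassignment but have no escalation split. The randomised schemes are therefore not compared within escalation.

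**4. Size of the understatement (illustrative).** The documents give no AE rates by step, so there is no planned figure to reproduce. Let p be the share of patients with the term in the shared weeks; by randomised arm it has the same expected value in each, because the doses are identical. Let q be the risk after divergence. If the two are independent:

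20-week risk = 1 - (1-p)(1-q), so the 20-week difference = (1-p)(qD - qC).

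Assume qC = 20%, qD = 40% and 70 patients per arm. As a measure of information only, z = difference / sqrt{[rC(1-rC) + rD(1-rD)]/70}, where rC and rD are the tabulated risks.

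| p | C, 20 weeks | D, 20 weeks | Difference | Ratio | z |
|---|---|---|---|---|---|
| weeks after divergence only | 20% | 40% | 20 points | 2.00 | 2.65 |
| 20% | 36% | 52% | 16 points | 1.44 | 1.93 |
| 40% | 52% | 64% | 12 points | 1.23 | 1.45 |
| 60% | 68% | 76% | 8 points | 1.12 | 1.06 |

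If the same patients tend to have events early and late, more is lost. With a logit-normal patient effect of SD 1 or 2 and p = 40%, 46% or 53% of the difference disappears, instead of 40%. If early events make late ones less likely, for instance because those patients have stopped, less is lost.

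**The case against.** The strongest reply is that a future patient would take the whole scheme, shared weeks included, so the risk of ever having nausea over 20 weeks is a proper summary. That stands. Onset after divergence is a further question, not a correction of a wrong answer. A reader might infer that the planned table is biased or will lead to the wrong scheme; the documents do not support that.

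Second, the scheme objective appears in one synopsis clause. Protocol sections 2.1.1 and 7 stress dose response and dose selection, and section 4.1.2 points to dose-exposure-response modelling of safety and efficacy as the basis for choosing a regimen. The Amendment 3 entry also describes exploratory modelling of nausea and vomiting at the interim. This shows that the AE tables are not the only route to a decision. But the SAP places the interim in a separate plan, and such modelling does not replace a randomised comparison in the final report.

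Third, each scheme ends at a different maintenance dose, so scheme and dose are confounded by design. No table can compare two schemes for the same target dose. That limits any display, including the one proposed below.

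Fourth, the rates above are assumed and no AE testing is planned. The benchmark z of 2.65 keeps 70 per arm; with an assumed 60 still on drug it would be 0.20 / sqrt(0.40/60) = 2.45. This is fair, and the figures show direction and rough scale only.

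Finally, parts of the SAP and of the further endpoints are not public. A reader might infer that no step-level tolerability output exists anywhere; only its absence from the visible text can be stated.

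**Conclusion.** The point holds as a gap in the descriptive safety outputs. In the visible SAP 7.8.1, no AE display isolates the weeks in which B, C and D differ, and none compares the randomised schemes within escalation. Both follow from the dose table and the tabulation rules and need no assumption.

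The extent to which the 20-week incidence understates later differences does rest on assumptions: the factor is (1-p) under independence, and the documents give no value for p. The Kaplan-Meier plot and disposition by period reduce the gap for events that stop treatment, but not for tolerated or recurrent gastrointestinal events. This is a cheap improvement in support of a stated objective.

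**What to change.** In SAP 7.8.1:

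- Add descriptive tables by planned (randomised) scheme for at least nausea, vomiting and diarrhoea, with onset in weeks 1-8, 9-12 and 13-20.
- Count each patient once per block, by new onset or recorded worsening in that block. Counting events merely present would carry early nausea into later blocks and bring the dilution back.
- Give two denominators: all treated patients, and patients still on drug at the start of the block. Show B, C and D pooled as well as separately for weeks 1-8.
- Present the existing escalation-period AE tables by planned treatment too.
- Because titration is flexible from week 11, calendar blocks do not identify the dose taken. Add a table or listing by actual dose at onset.

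The cost is SAP wording and a few tables built from AE onset dates and dosing records already collected; no dose, visit or error rate changes. The drawbacks are small counts per block and, with the on-drug denominator, later blocks that compare selected patients. Those tables should be labelled descriptive only.
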